2.3 Composite primary efficacy endpoint

The primary efficacy endpoint is the cumulative rate of any stroke or death from any cause within 30 days plus ipsilateral ischemic stroke within 5 years of follow up.

The primary effect expected from surgery or stenting is to reduce hemodynamic or thromboembolic ischemia of ipsilateral brain tissue. The clinically relevant figure is the sum of periprocedural complications and ipsilateral ischemia during a longer period. Conservative treatment is expected to go along with low 30-day complication rates but higher long-term ipsilateral ischemia rates. The reverse is to be expected with surgery

and stenting. The efficacy endpoint takes into account both components. This endpoint has been used in many previous carotid stenosis trials [7-8, 16].

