4.5 Criteria for withdrawal

4.5.1 Withdrawal of subjects

A subject may be withdrawn from all trial related procedures (including follow-up visits) for the following reasons:

at his/her own request or at request of his legal representative

non-adherence to the trial-related requirements, which may (have) influence(d) the validity of the trial data

If, in the investigator's opinion, continuation of the trial would be detrimental to the subject's well-being, e.g. if a patient was randomized into the BMT arm and suffers ipsilateral neurological symptoms, patient treatment based on actual guidelines either with CEA or CAS

Occurrence of exclusion criteria

If, in the investigator's opinion, protocol violations caused by the subject would lead to invalid data (e.g. non-compliance with planned study procedures).

The Executive Committee (see chapter 10.2) decides about withdrawal of subjects from trial treatment in case of occurrence of criteria mentioned above. A withdrawn patient will be treated as censored at time of leaving the study.

In all cases, the reason for withdrawal must be recorded in the CRF and in the subject's medical records. In case of withdrawal of a subject at his/ her own request, the reason should be asked for as extensively as possible and documented. All efforts will be made to follow up the subject and, all examinations scheduled for the final trial day will be performed as far as possible on all subjects and documented. All ongoing Adverse Events (AEs) / Serious Adverse Events (SAEs) of withdrawn subjects have to be followed up until no more signs and symptoms are verifiable or the subject is on stable condition.

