5 TRIAL PROCEDURES

5.1 Description of trial days

Study visits are scheduled as follows:

Screening

Randomization (Screening and randomization can be done on the same day, must be done within 14 days after screening)

Therapy [=day 0] (if randomized to CAS or CEA, must be within 28 days after randomization)

Day 1 \pm 0 after therapy (if randomized to CAS or CEA)

30 \pm 3 days after randomization (if randomized to BMT) resp. after therapy (if randomized to CAS or CEA)

6 months \pm 7 days after randomization

1 year \pm 14 days after randomization

2 years \pm 14 days after randomization

3 years \pm 28 days after randomization

4 years \pm 28 days after randomization

5 years \pm 28 days after randomization

An overview about the procedures to be done at specific visits can be found on page 9.

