5.5 Follow-up examinations

The duration of the trial for each subject is 5 years. After the periprocedural phase yearly examinations are scheduled. Each visit consists of an event-screening, a risk-factor screening, and an ultrasound-examination.

The 30day visit for patients randomized into the BMT-arm is primarily used to evaluate if the recommendations for risk-factor-modification have been fulfilled.

Events are screened using a standardized questionnaire. An event has occurred if one of the following questions has been answered positively:

„Ist (seit der letzten Untersuchung) eine vorübergehende Sehstörung auf einem Auge aufgetreten?“

„Ist (seit der letzten Untersuchung) eine Schwäche oder Sensibilitätsstörung auf einer Körperseite aufgetreten?“

„Ist (seit der letzten Untersuchung) eine Sprachstörung aufgetreten?“

„Haben sich (seit der letzten Untersuchung) neue Beschwerden entwickelt?“

If a cerebrovascular outcome-event occurred an appropriate neuroimaging should be performed to distinct between possible types of stroke. In addition the mRS and NIHSS have to be assessed and documented. 30 days after symptom onset the patient has to be contacted to assess the mRS at this time point. In case of an ipsilateral cerebrovascular event in a subject randomized into the BMT-arm, patient should be considered for CEA or CAS following actual guidelines for treatment of symptomatic stenosis.

Risk-factor screening, assessment of medication, and ultrasound-examinations has to be done at any follow-up visit like described above (section 5.2)

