6 ASSESMENTS

6.1 Definitions

Ischemic Stroke: New focal neurological deficit of vascular origin lasting more than 24 hours, absence of intracranial hemorrhage upon brain imaging.

Hemorrhagic Stroke: New focal neurological deficit of vascular origin lasting more than 24 hours, proof of intracranial hemorrhage upon brain imaging.

Ipsilateral stroke: Stroke within the territory of the treated carotid artery.

Disabling stroke: Stroke leading to a disability of at least 3 on the modified Rankin scale at day 30±3 after symptom onset.

Myocardial infarction: Detection of rise and/or fall of cardiac biomarkers (preferable troponin) with at least one value above the 99th percentile of the upper reference limit together with evidence of myocardial ischemia with at least one of the following [21]

- Symptoms of ischemia
- ECG changes indicative of new ischemia (new ST-T changes or new left bundle branch block (LBBB))
- New onset of pathological Q waves in ECG
- Imaging evidence of new loss of viable myocardium or new regional wall motion abnormality

Vascular death: Deaths due to stroke, myocardial infarction, or hemorrhage as well as any deaths those were not clearly non-vascular.

Technical failure: Inability to treat the stenosis with the allocated method or remaining stenoses of at least 70% following ultrasound-criteria at day 1.

Restenosis: Recurrent stenosis of at least 70% following ultrasound-criteria, which will be defined in the 'Neurology quality appendix'.

Observation period: 30 day endpoints for patients randomized into the BMT-group are evaluated after 30±3 days after randomization. 30 days risks for patients randomized into the CAS or CEA-arm are evaluated between randomization and 30±3 days after the procedure. Medium-term (up to 2 years) observational period's starts at the time of randomization, assessment can be done in a time period ±14 days around the calculated date. Long-term (up to 5 years) observational period's starts at the time of randomization, assessment can be done in a time period ±28 days around the calculated date.

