6.3 Evaluation of efficacy

6.3.1 Primary endpoint

The primary efficacy endpoint is the cumulative rate of any stroke (ischemic or haemorrhagic) or death from any cause within 30 days plus ipsilateral ischemic stroke within 5 years of follow up.

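### A death or non-ipsilateral-ischaemic stroke caused by a later CEA or CAS in the BMT arm is not a primary event, although the same complication of an allocated procedure is

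*Protocol*

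**What the plan says.** Section 6.3.1 defines the primary endpoint as "any stroke (ischemic or haemorrhagic) or death from any cause within 30 days plus ipsilateral ischemic stroke within 5 years of follow up". Sections 2.3 and 9.2 say the same. After the early window, only ipsilateral ischaemic stroke counts.

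Section 6.1 sets the early window by arm. For BMT: "30 day endpoints for patients randomized into the BMT-group are evaluated after 30±3 days after randomization". For the interventions: "30 days risks for patients randomized into the CAS or CEA-arm are evaluated between randomization and 30±3 days after the procedure". Section 5.1 adds that the allocated procedure "must be within 28 days after randomization", so the intervention window can reach day 28 + 33 = 61.

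Section 5.5 foresees procedures in the BMT arm: "In case of an ipsilateral cerebrovascular event in a subject randomized into the BMT-arm, patient should be considered for CEA or CAS". Section 4.5.1 describes the same patient as an example of a reason for withdrawal ("if a patient was randomized into the BMT arm and suffers ipsilateral neurological symptoms", then CEA or CAS) and censors withdrawn patients when they leave. Section 9.3 makes the primary analysis intention-to-treat (ITT). Section 2.3 gives the endpoint's rationale: "The clinically relevant figure is the sum of periprocedural complications and ipsilateral ischemia during a longer period".

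**The concern.** Under ITT, the BMT arm represents a strategy: medical treatment now, with a procedure later if one becomes indicated. The complications of that later procedure belong to the strategy. The stated rationale is to add periprocedural harm to later ipsilateral ischaemia, yet the window follows the procedure in the CEA and CAS arms and follows randomisation in BMT. No section opens a window for a deferred procedure.

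The trigger for a deferred procedure need not be a primary event. Section 6.1 requires a deficit lasting more than 24 hours for a stroke, while the event questionnaire in section 5.5 also picks up transient visual loss in one eye. A BMT patient can therefore have a TIA, undergo CEA or CAS, die from it, and be analysed as free of the primary endpoint. If the withdrawal route in section 4.5.1 is used, a procedural ipsilateral ischaemic stroke can be lost as well. At stake is a modest understatement of BMT risk in the primary comparison of each substudy.

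**Working it through.** **The plan's own figure.** Section 9.1 (amended text) gives hazards of 0.01 and 0.005 per year, hazard ratio 0.50, two-sided 5%, power 80%, accrual 5 years and follow-up 3 years.

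- Events (Schoenfeld): 4 × (1.960 + 0.842)² / (ln 0.5)² = 65.3.
- Event probability with uniform accrual: 1 − [exp(−3λ) − exp(−8λ)] / (5λ) = 0.0534 for BMT and 0.0271 for intervention; the mean is 0.0403.
- Total: 65.35 / 0.04026 = 1,623. Multiplied by about 1.008 for a two-look O'Brien-Fleming design, this gives 1,636, as stated.
- Expected BMT events among 818 patients: 818 × 0.0534 = 43.7. If each patient contributes exactly 5 years, 818 × (1 − exp(−0.05)) = 39.9 for BMT and 818 × (1 − exp(−0.025)) = 20.2 for intervention.

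**Which complications count, reading sections 4.5.1, 5.5, 6.1 and 6.3.1 together.**

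1. Any stroke or death in the window after the allocated CEA or CAS: counted.
2. BMT patient with an ipsilateral ischaemic stroke, then a procedure with a complication: the first primary event has already occurred, so a time-to-first-event analysis loses nothing.
3. BMT patient with a TIA, then a late procedure causing an ipsilateral ischaemic stroke: counted under the 5-year component, unless the patient was withdrawn and censored.
4. BMT patient with a TIA, then a late procedure causing death or a haemorrhagic or contralateral stroke: not counted.
5. CEA or CAS patient with a repeat procedure after the window and a complication as in case 4: not counted.

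**Size of case 4.** Uncounted BMT events per substudy: m = 818 × c × r × s.

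- c: share of BMT patients treated after the window without a prior primary event. The protocol gives no figure; 5% and 10% are assumed, with 20% for comparison.
- r: procedural stroke or death risk, from 2.9% (meta-analysis figure, section 1.1.3) to 6% (ceiling for symptomatic stenosis, section 1.1).
- s: share of complications other than ipsilateral ischaemic stroke; 25% to 50% is assumed.

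| c | lowest m | highest m | share of 39.9–43.7 BMT events |
|---|---|---|---|
| 5% | 818 × 0.05 × 0.029 × 0.25 = 0.30 | 818 × 0.05 × 0.06 × 0.50 = 1.23 | 0.7–3.1% |
| 10% | 0.59 | 2.45 | 1.4–6.2% |
| 20% | 1.19 | 4.91 | 2.7–12.3% |

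**Effect on the hazard ratio** (5-year basis): 0.025 / −ln(1 − (39.9 ± m)/818). If the planned 0.01 per year already includes these events, leaving them out moves 0.50 to between 0.504 (m = 0.30) and 0.534 (m = 2.45). If it excludes them, counting them moves 0.50 to between 0.496 and 0.470.

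**Offset from case 5.** At the planned rates, one lost intervention event is 1/20.2 = 5.0% of that arm's events, and one lost BMT event is 1/39.9 = 2.5%. At equal r and s, late re-intervention in half as many patients as BMT crossover would cancel the effect. For example, losing 2.45 BMT events (c = 10%) and 1.23 intervention events (5%) gives a hazard ratio of about 0.50. The protocol gives neither rate.

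**The case against.** The endpoint is worded consistently in sections 2.3, 6.3.1 and 9.2, and section 6.1 fixes its windows. Limiting late events to ipsilateral ischaemic stroke is a deliberate choice, and section 2.3 says earlier carotid trials used this endpoint. Reopening an any-stroke-or-death window at every procedure would define a different estimand, with windows triggered by post-randomisation decisions in an open trial. The secondary endpoints in section 6.3.2 include any stroke, and any stroke or vascular death, up to 5 years. Because section 6.1 treats any death not clearly non-vascular as vascular, most of these events would be reported there.

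Much of this stands. The text does not require a new primary endpoint. The secondary endpoints make the events visible, but the primary test does not use them.

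A reader might go further and infer that the rule loses every crossover complication, removes more than a tenth of BMT events and clearly biases both substudies against intervention. The documents do not support that. Crossover after a primary event loses nothing, and a procedural ipsilateral ischaemic stroke still counts unless the patient is censored. A loss of 11–12% needs 20% crossover without a prior primary event, the 6% ceiling and the 50% share all at once. Re-intervention complications go uncounted in the CEA and CAS arms, which works in the opposite direction.

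The withdrawal route in section 4.5.1 is optional, and that section also asks for efforts to follow withdrawn patients. Even so, it names this patient and then censors.

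**Conclusion.** The asymmetry is real and follows from the text. BMT patients who have a deferred CEA or CAS without a prior primary event can die or have a haemorrhagic or contralateral stroke from it without counting. This departs from the rationale in section 2.3 and tends to favour BMT, provided late re-intervention in the other arms is less than about half as frequent as BMT crossover.

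Under the assumed 5–10% crossover, the loss is about 0.3 to 2.5 BMT events per substudy, roughly 1–6% of 40–44; it is larger only at higher crossover. The crossover rate and the share of uncounted complication types are assumptions, because the protocol gives neither. The gap justifies a sensitivity analysis and consistent follow-up rules. It does not invalidate the primary analysis.

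**What to change.** 1. Pre-specify a sensitivity analysis of the primary endpoint, identical in all arms, that also counts any stroke or death from any cause within 30 days after any CEA or CAS of the randomised artery during the 5-year follow-up, whether a deferred procedure or a re-intervention. If the SAP already holds this analysis, a cross-reference in section 9.4 is enough.
2. Reconcile sections 4.5.1, 5.5, 6.1 and 6.3.1 so that a BMT patient who receives CEA or CAS stays in follow-up and in the ITT analysis and is not censored because of the procedure. This concerns counting and follow-up only, not whether or when such a patient is treated.

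The cost is low. Suspected strokes and all deaths already go to the endpoint committee (section 6.4), outcome events and serious adverse events are reported within 24 hours (sections 7.3 and 7.4), and concomitant surgical treatment is recorded (section 4.7).

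There are three drawbacks. Some unrelated deaths after a procedure will count. The added windows depend on post-randomisation decisions in an open trial, which is why this suits a sensitivity analysis. The 30-day status after crossover must come from existing event reports, because section 5.1 schedules procedure-timed visits only for patients randomised to CEA or CAS.

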6.2 Evaluation of Safety

Safety is assessed as the rate of any stroke and death from any cause within 30 days of treatment. This safety endpoint will only evaluate in patients randomized to CEA or CAS.

6.3 Evaluation of efficacy

6.3.1 Primary endpoint

The primary efficacy endpoint is the cumulative rate of any stroke (ischemic or haemorrhagic) or death from any cause within 30 days plus ipsilateral ischemic stroke within 5 years of follow up.

6.3.2 Secondary endpoints

All single components of the primary endpoint clusters

Any stroke, death or myocardial infarction within 30 days

Any disabling stroke and death within 30 days

Any stroke up to 5 years since randomization

Any disabling stroke up to 5 years since randomization

Any stroke or vascular death up to 5 years since randomization

Ipsilateral ischemic stroke within 30 days and after 5 years since randomization

Ipsilateral disabling stroke within 30 days and after 5 years since randomization

Technical failure of intervention

Rate of re-stenosis ($\geq 70\%$ ^{ECST}) up to 5 years since randomization

Rate of myocardial infarction at 30 days after the procedure in patients randomized to CAS or CEA

6.3.3 Tertiary endpoints

All primary and secondary endpoints will also be assessed after 1 and 3 years since randomization.

6.4 Endpoint evaluation

All suspected strokes, as well as all myocardial infarctions, and all deaths will be evaluated by a committee of experts blinded to treatment, who will determine the final classification of these events. This committee, named 'endpoint evaluation committee' is described in section 10.3 at page 40.

7 ADVERSE EVENT REPORTING

7.1 Definitions

7.1.1 Adverse event

According to GCP, an adverse event (AE) is defined as follows: Any untoward medical occurrence in a subject administered a pharmaceutical product and which does not necessarily have a causal relationship with this treatment. An AE can therefore be any unfavorable and unintended sign (including an abnormal laboratory finding), symptom, or disease temporally associated with the use of a medicinal (investigational) product, whether or not related to the medicinal (investigational) product.

An AE may be:

New symptoms/ medical conditions

New diagnosis

Changes of laboratory parameters

Intercurrent diseases and accidents

Worsening of medical conditions/ diseases existing before clinical trial start

Recurrence of disease

Increase of frequency or intensity of episodically diseases.

A pre-existing disease or symptom will not be considered an adverse event unless there will be an untoward change in its intensity, frequency or quality. This change will be documented by an investigator.

Surgical procedures themselves are not AEs; they are therapeutic measures for conditions that require surgery. The condition for which the surgery is required may be an AE. Planned surgical measures permitted by the clinical trial protocol and the condition(s) leading to these measures are not AEs, if the condition leading to the measure was present prior to inclusion into the trial.

AEs are classified as "non-serious" or "serious".

7.1.2 Serious adverse event

A serious adverse event (SAE) is one that at any dose:

Results in death

Is life-threatening (the term life-threatening refers to an event in which the subject was at risk of death at the time of event and not to an event which hypothetically might have cause death if it was more severe)

Requires subject hospitalization or prolongation of existing hospitalization

Results in persistent or significant disability/ incapacity or

Is a congenital anomaly/ birth defect.

7.1.3 Expectedness

An 'unexpected' adverse event is one the nature or severity of which is not consistent with the trial procedures. Furthermore, reports which add significant information on specificity or severity of a known adverse reaction constitute 'unexpected' events.

7.1.4 Outcome event

Outcome events are the components of the endpoints (see chapter 6.3). Most of these will also be SAEs.

7.2 Period of observation and documentation

All AEs reported by the subject or detected by the investigator, will be collected during the trial and must be documented on the appropriate pages of the CRF. AEs must also be documented in the subject's medical records.

In this trial, all AEs that occur after the subject has signed the informed consent document will be documented on the pages provided in the CRF. All subjects who have AEs, whether considered associated with the use of the trial medication or not, must be

monitored to determine the outcome. The clinical course of the AE will be followed up until resolution or normalization of changed laboratory parameters or until it has changed to a stable condition.

The intensity of an AE should be assessed by the investigator as follows:

- Mild: temporary event which is tolerated well by the subject.
Moderate: event which results in discomfort for the subject and impairs his/her normal activity.
Severe: event which results in substantial impairment of normal activities of subject.

The grading of AEs in this trial will be carried out on the basis of the 5-grade scale defined in the CTCAE v3.0:

- Grade 1: mild AE
Grade 2: moderate AE
Grade 3: severe AE
Grade 4: life-threatening AE or AE causing disablement
Grade 5: Death related to AE

The grading of all AEs listed in the CTCAE v3.0 will be based on the information contained therein. The grading of all other AEs, i.e. those which are not listed in the CTCAE v3.0 will be performed by a responsible investigator, based on definitions given above.

The investigator will evaluate each AE that occurred after administration of investigational medicinal product regarding the coherency with the administration of the investigational medicinal product possibly:

- Related: There is a reasonable possibility that the event may have been caused by IMP. A certain event has a **strong temporal relationship** and an alternative cause is unlikely.
- probable: An AE that has a reasonable possibility that the event is likely to have been caused by IMP. The AE has a **timely relationship** and **follows a known pattern of response**, but a potential alternative cause may be present.
- possible: An AE that has a reasonable possibility that the event may have been caused by IMP. The AE has a **timely relationship** to the IMP; **however, the pattern of response is untypical**, and an alternative cause seems more likely or there is significant uncertainty about the cause of the event.
- unlikely: Only a remote connection exists between the IMP and the reported adverse event. Other conditions including concurrent illness, progression or expression of the disease state or reaction of the concomitant medication appear to explain the reported adverse event.
- not related: An AE that does not follow a reasonable temporal sequence related to IMP and is likely to have been produced by the subject's clinical

state, other modes of therapy or other known etiology.

not assessable: The relationship between an AE and the IMP that does not follow a reasonable temporal sequence from trial participation and that is likely to have been produced by the subject's clinical state, other modes of therapy or other known etiology.

The outcome of an AE at the time of the last observation will be classified as:

recovered/ resolved:	all signs and symptoms of an AE disappeared without any sequels at the time of the last interrogation
recovering/ resolving:	the intensity of signs and symptoms has been diminishing and/ or their clinical pattern has been changing up to the time of the last interrogation in a way typical for its resolution
not recovered/ not resolved:	signs and symptoms of an AE are mostly unchanged at the time of the last interrogation
recovered/ resolved with sequel:	actual sings and symptoms of an AE disappeared but there are sequels related to the AE.
fatal:	resulting in death. If there are more than one adverse event only the adverse event leading to death (possibly related) will be characterized as 'fatal'
unknown:	the outcome is unknown or implausible and the information cannot be supplemented or verified

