1.3 Benefit / risk assessment

The benefit from every treatment modality is the proposed reduction of future cerebro- and also cardiovascular events. However, each treatment arm carries specific risks. Risks from the conservative treatment are mainly due to possible side effects of the used medication. Most feared risk of both CAS and CEA is the risk of periprocedural stroke. Differences between the risk of CAS and CEA are based on technical details. CEA is usually performed under general anesthesia, which might contribute to the procedure related complication rate, up to now only a few centers offer local anesthesia as an alternative. In contrast CAS is generally performed under local anesthesia, general anesthesia is only required in patients with poor cooperation. CAS always needs interventional angiography, which increases the risk of stroke by 0.1–0.3% [7]. Current experience suggests that CAS without embolic protection devices causes more microembolic events than does CEA and these events seem to be associated with an increased risk of postinterventional DWI lesions, however the clinical impact of these lesions is still under discussion [13]. Although CAS causes fewer cranial nerve lesions, it might be associated with more-frequent restenoses than CEA.

To minimize these risks every individual in the trial will be treated by named experts and a close monitoring for such events will be done. In addition both endarterectomy and

stenting will be done only by certified physicians with a high level expertise and continuous quality control. For any treatment modality quality committees are defined. These committees define the rules for the treatment and the quality control criteria (see Appendix).

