3 TRIAL DESIGN

OLD: SPACE-2 is a randomized, controlled, open, multi-center study with three parallel groups:

Best medical treatment (BMT)

Carotid endarterectomy (CEA) + BMT

Carotid artery stenting (CAS) + BMT

A hierarchical study protocol has been developed with a superiority design of intervention vs. conservative treatment. In case superiority for CAS and CEA is established, a non-inferiority comparison between the two interventions will be performed.

NEW: SPACE-2 is a randomized, controlled, open, multi-center study with two parallel substudies:

- SPACE2a: CEA vs. BMT
- SPACE2b: CAS vs. BMT

Primary aim of the study is to compare BMT with any type of intervention (CEA or CAS). In addition, data from the CEA and CAS-groups will be compared in an explorative manner. In order to analyze the effect between the two interventional methods, an indirect treatment comparison will be applied [17].

All patients are treated with a best medical treatment regimen tailored to their individual risk factor profile consisting in treatment of risk factors, lipid-lowering and anti-platelet medication. Rules for the BMT will be formulated by the BMT-subcommittee and are an appendix to this protocol.

The overall duration of the trial is expected to be approximately 9 years. Recruitment of subjects will start in October 2008. The actual overall duration of recruitment may vary.

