7.3 Reporting of SAEs by investigator

All SAEs must be reported by the investigator within 24 hours after the SAE becomes known using the 'Serious Adverse Event' form to the Data Management. The initial report must be as complete as possible including details of the current illness and (serious) adverse event and an assessment of the causal relationship between the event and the trial procedures.

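### Section 7.2 rates adverse-event causality against an undefined medicinal product while 7.3 uses the trial procedures, and *not assessable* is defined like *not related*

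*Protocol*

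**What the plan says.** Protocol section 7.2 sets the causality rule: "The investigator will evaluate each AE that occurred after administration of investigational medicinal product regarding the coherency". Six categories follow, from *related* to *not assessable*, and each is worded around that product. Two of them matter most here:

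- *Not related* is given as "An AE that does not follow a reasonable temporal sequence related to IMP and is likely to have been produced by the subject's clinical". The definition ends by listing the patient's condition, another therapy or another known cause.
- *Not assessable* is given as "The relationship between an AE and the IMP that does not follow a reasonable temporal sequence from trial participation". It ends with the same list of alternative explanations.

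Section 7.3 requires the initial report of a serious adverse event to contain "an assessment of the causal relationship between the event and the trial procedures". Section 7.1.3 likewise judges expectedness against the trial procedures.

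Section 3 gives the randomized comparisons as "SPACE2a: CEA vs. BMT" and "SPACE2b: CAS vs. BMT". It adds that medication is common to all arms: "All patients are treated with a best medical treatment regimen tailored to their individual risk factor profile".

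**The concern.** The treatments that differ between arms are a surgical and a stenting procedure, but the 7.2 scale asks whether a medicinal product caused the event. The protocol itself expects harms that are specific to one procedure. Section 1.3 states "Although CAS causes fewer cranial nerve lesions, it might be associated with more-frequent restenoses than CEA" and discusses anesthesia as a possible source of complications, and section 1.2 mentions wound healing. Cranial nerve and wound events are not listed endpoints. When they are not serious, they reach the data through the adverse-event pages.

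At stake is whether a table of treatment-related adverse events can be read. If each of the roughly 100 centers has to decide for itself what the product is, and whether *not assessable* means unknown or no, the relatedness column will mix different judgments. The investigator makes this rating at data entry, so an analysis plan written later cannot repair it.

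**Working it through.** No sample size, power or error-rate figure is involved, so the check is a comparison of the passages.

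**Step 1: the object of the rating.**

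| Section | What is judged | Against what |
|---|---|---|
| 7.1.3 | expectedness of an adverse event | trial procedures |
| 7.2 | causality of each adverse event | investigational medicinal product |
| 7.3 | causality of each serious adverse event | trial procedures |

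The abbreviation list has no entry for IMP. Nothing in the protocol text at hand designates a treatment as one. Section 7.2 also speaks of a trial medication without defining it.

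**Step 2: can the product be read as the BMT drugs?** This is the only reading that gives the term content. Under section 3, BMT is given in every arm, so the scale would rate the common medication and never the procedure that distinguishes the arms. CEA or CAS would then be another therapy, which the definition of *not related* counts as an alternative cause. A nerve lesion plainly caused by CEA would satisfy that part of the definition. On this reading too, no category names the procedure.

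**Step 3: serious events.** Section 7.1.1 divides adverse events into serious and non-serious, so a serious event is also one of the events that 7.2 wants rated. It can be unrelated to the product under 7.2 and related to the procedure under 7.3, with both answers correct as asked. No rule says which one counts.

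**Step 4: *not related* against *not assessable*.**

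| Element | *Not related* | *Not assessable* |
|---|---|---|
| Timing | no plausible sequence with the product | no plausible sequence with trial participation |
| Likely cause | clinical state, other therapy, other known cause | the same three |
| Missing information mentioned | no | no |

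Only the reference of the timing clause differs. Deciding that timing does not fit and that another cause is likely is itself an assessment, so the definition contradicts its label. The same section defines the outcome category *unknown* properly, by information that cannot be completed or verified.

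**Step 5: what depends on the scale.** Section 7.2 requires all adverse events after consent to be documented whatever their relatedness. Section 6.2 counts any stroke and any death within 30 days in the CEA and CAS patients. Section 6.3.2 counts myocardial infarction at 30 days after the procedure and technical failure. The stopping criteria in 4.5.3 and 9.4 use the 30-day stroke or death rate. None of these needs a causality rating.

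**The case against.** The strongest reply is that the important procedural harms never pass through the 7.2 scale. Stroke, death, myocardial infarction and technical failure are counted by arm, and section 6.4 sends suspected strokes, infarctions and deaths to a blinded committee. Serious events get a procedure-based assessment under 7.3, and an event that prolongs hospitalization is serious under 7.1.2. Every adverse event is recorded, so arms can be compared without any relatedness label. All of this stands, and it limits the point.

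A second reply is that *possible* already covers significant uncertainty about cause. This stands in part: that category still requires a fitting time relation to the product, so an event with unknown timing does not belong there.

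Three stronger readings are tempting, and the documents do not support them:

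- A reader might infer that procedural harm is not attributed to CEA or CAS at all, or is under-reported. Section 7.3 contradicts the first, and the full documentation duty in 7.2 contradicts the second.
- A reader might infer that no medicinal product exists and that literally no event is rated. The text at hand shows only that none is defined. The BMT procedures are in an appendix that is not available.
- A reader might multiply an assumed complication rate by the 818 patients planned per arm to count mislabeled events. The protocol gives no rate for non-serious nerve or wound events, so such a count would have no source.

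**Conclusion.** The point holds at limited scope. As written, 7.2 and 7.3 use different causal references, the reference in 7.2 is undefined, and *not assessable* has practically the same definition as *not related*. A non-serious procedural event can therefore be labeled *not related* by following the text, and a serious one can carry two ratings that differ.

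The consequence is confined to relatedness labels of non-serious adverse events and to consistency of serious-event causality between the two sections. Collection of adverse events, the primary endpoint, the 30-day safety endpoint and the stopping rule are unaffected. The number of mislabeled events cannot be derived from the protocol.

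The conclusion assumes that the appendices do not define the product. It also assumes that the electronic case report form, which was not seen, follows the wording of 7.2. The duplicated definition is a fault whatever the appendices say.

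**What to change.** In 7.2, replace the medicinal product and its abbreviation throughout by the allocated trial treatment: the CEA or CAS procedure and, if intended, BMT medication, with the investigator stating which is meant. Use the same reference in 7.3, so that a serious event has one causal object.

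Redefine *not assessable* as information that is insufficient or contradictory and cannot be supplemented, and tabulate it separately from *not related*.

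The cost is protocol wording, matching labels in the electronic case report form, and one query round for adverse events already rated. Sample size, endpoints and visits do not change.
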